1. BACKGROUND AND RATIONALE

1.1 Disease

The ichthyoses are a group of lifelong genetic disorders which share characteristics of skin thickening, scaling and underlying cutaneous inflammation. Other than ichthyosis vulgaris (commonly associated with atopic dermatitis) and recessive X-linked ichthyosis (1:1500 boys), the >20 subtypes of ichthyosis are rare (<1:100,000 individuals). Among these rare subtypes are 3 predominant forms: i) epidermolytic ichthyosis, resulting from a mutation in one of the genes encoding suprabasal keratins; ii) Netherton syndrome, resulting from mutations in SPINK5, leading to excessive epidermal protease activity; and iii) autosomal recessive congenital ichthyosis (ARCI). This last group usually first manifests at birth as a collodion baby (Figure. 1A), in which a shiny “collodion-like” membrane encases the neonate. Within the first month of life, this membrane skin peels, revealing during the subsequent months a generalized skin

Product: Secukinumab

Protocol Number: CAIN457AUS05T

Date: 14 July 2018

12

appearance ranging from variable redness (erythema) underlying darker, plate-like scaling (lamellar ichthyosis or LI, Fig. 1B) to intense erythema with fine scaling (congenital ichthyosiform erythroderma or CIE, Figure. 1C). Biallelic mutations, largely in genes encoding epidermal lipoygenases, ichthyin, transporter ABCA12, and transglutaminase 1, lead to the ARCI phenotype. All ichthyosis types share a defective protein and lipid barrier, which manifests functionally as increased transepidermal water loss and percutaneous absorption.

These forms of ichthyosis lead to life-long disfigurement due to the highly visible erythema and scaling. The quality of life of affected children and adults is poor, not only because of their appearance and social ostracism, but also because of the frequent associated itchiness (pruritus) and functional limitations related to the inflamed, often fissured skin and limited joint mobility related to skin tightness and pain. Affected individuals also have a markedly reduced ability to sweat, restricting sports and outdoor activities in warmer weather.

Therapy for the ichthyoses is supportive and time-consuming for patients. Most use long baths, emollients and agents that peel the thick scale, specifically keratolytics and topical retinoids. Oral retinoids are most effective at removing scale and skin thickening, but tend to increase skin and mucosal inflammation and have potential side effects (most commonly hypertriglyceridemia, teratogenicity, and with chronic use hyperostosis). The high risk of systemic absorption of topical steroids (and side effects of systemic steroids) restricts their use for the cutaneous inflammation associated with these lifelong diseases. There remains a huge unmet need for more effective and safer treatments, ideally therapy that improves both the scaling and the cutaneous inflammation with its associated pruritus and discomfort.

1.2 IL-17 in Ichthyosis

While the underlying gene mutations in most forms of ichthyosis are now well delineated, explaining at least in part the barrier defect, the molecular mechanism underlying the inflammation and the skin thickening and scaling, which is presumed to be compensatory, is poorly understood. To explore the immune basis for the erythroderma, we have recently surveyed the skin of individuals with ichthyosis of known underlying genotype, characterized clinically as ARCI, Netherton syndrome or epidermolytic ichthyosis. Interestingly, all studied forms of ichthyosis showed a biomarker pattern in skin of Th17 immune skewing (Fig. 2). In these patients, the mRNA expression levels of IL-17A and other IL-17 induced genes (such as S100A's, CXCL1, CCL20, and PI3/elafin) was dramatically increased in contrast to normal skin, and almost as high and sometimes higher than that seen in lesional skin from individuals with psoriasis, a common skin disorder in which the erythema and increased scaling are now recognized to be driven by Th17. In psoriasis, neutralization of IL-17 by specific IL-17A antagonism leads to 75% disease reversal ("PASI75") in 93% of treated subjects by 16 weeks (Thaci et al 2015) and is the most effective intervention to date for psoriasis (Nast et al 2015). Antagonism of this "polar" cytokine pathway seems to produce fewer adverse effects compared to broader immune antagonism (Thaci et al 2015); (Nast et al 2015); (Langley et al 2014).

1.3 Clinical Hypotheses

We hypothesize that Th17 activation plays an important role in the erythema and possibly the thickening and scaling of ichthyosis. Furthermore, we posit that IL-17-targeting therapeutics will safely suppress the inflammation and possibly the other features, improving quality of life. We propose to treat adults with

Product: Secukinumab

Protocol Number: CAIN457AUS05T

Date: 14 July 2018

13

ARCI and at least moderate erythema with subcutaneously administered anti-IL-17 antibody (secukinumab) and serially assess clinical response to therapy and its safety. Throughout the course of the intervention, we will sample blood and skin biopsies, which will support our interpretation of result and allow us to perform more comprehensive mechanistic studies. We hypothesize that: a) intervention with anti-IL-17 antibody therapy (secukinumab) will improve ARCI severity as a function of IL-17 suppression; and b) the administration of secukinumab will be well-tolerated.

1.4 Rationale for Secukinumab Use

This proposal takes a commercially available medication that is indicated for a common IL-17-driven inflammatory skin disease (plaque psoriasis) and applies it to treat an orphan disease based on our innovative discovery that IL-17 levels correlate with severity in ichthyosis. Indeed, we have biopsied upper arm skin of >20 patients with the typical generalized features of ARCI, EI or Netherton syndrome and found dramatic increases in IL-17A and IL-17A-induced cutaneous markers in ichthyotic skin (Fig. 2A). Using a severity scoring system that rates overall score (Ichthyosis Area Severity Index or "IASI"), and subscores of erythema ("IASI-E") and scaling ("IASI-S") based on intensity (0-4+) and extent (see Approach), the composite IASI (total score) and IASI-E (Fig. 2B) are highly positively correlated with levels of IL-17A and related genes. IASI-E showed the highest correlations with IL-17A ($r=0.74$, $p<0.001$) and related genes, such as CXCL1 ($r=0.74$, $p<0.001$), PI3 ($r=0.71$, $p<0.001$), S100A8 ($r=0.71$, $p<0.001$), S100A9 ($r=0.69$, $p=0.001$), S100A12 ($r=0.68$, $p=0.001$), DEFB4B ($r=.56$, $p=.01$), and LCN2 ($r=0.5$, $p=0.02$). IASI-E is also correlated with transepidermal water loss (TEWL), a functional measure of barrier deficiency ($r=0.47$, $p=0.04$). IASI was also highly correlated with IL-17A ($r=0.51$, $p=0.01$), CXCL1, ($r=0.54$, $p=0.01$), PI3 ($r=0.69$, $p=0.001$), S100A8 ($r=0.67$, $p=0.001$), S100A9 ($r=0.62$, $p=0.002$), S100A12 ($r=0.58$, $p=0.006$), and LCN2, ($r=0.55$, $p=0.01$), as well as with IASI-E ($r=0.73$, $p<0.001$). In addition to IASI-E, TEWL showed significant correlations with IL-17 related markers (e.g., DEFB4 ($r=0.65$, $p=0.004$) and S100A12 ($r=0.62$, $p=0.009$)). Finally, K16, a marker of epidermal proliferation/hyperplasia also was highly positively correlated with IASI ($r=0.63$, $p=0.002$) and IASI-E ($r=0.56$, $p=0.008$). The biomarker alterations of ichthyosis cluster distinctly without subclustering by ichthyosis subtype; the clustering of ichthyosis closely resemble that of psoriasis and is distant from atopic dermatitis (Fig 2C).

Secukinumab is commercially available, administered subcutaneously (no oral formulation), and routinely administered at a dosage of 300 mg; in the first 4 weeks, a weekly dosage is standardly given, followed by monthly administration. This dosage for psoriasis was based on dose-finding studies and has been shown to be of superior efficacy to other biologics for psoriasis (Thaci JAAD 2015). Because the drug is already available commercially (for adults with psoriasis), significant clinical improvement in this first double-blind, randomized, controlled trial of a biologic for ichthyosis can translate into rapid availability for patients. However, the proposed work has several additional innovative dimensions. First, it will better define the relationship between increases in IL-17 and the cutaneous manifestations of ARCI. These insights will be critical to understanding whether IL-17 drives the erythema, pruritus and barrier defect (increased transepidermal water loss) of the ARCI group of ichthyoses. Our limited assessment in this proposal of the effect in skin of systemically-administered IL-17 antagonism will allow us to correlate clinical improvement with reduction in IL-17-induced products, which is key for interpreting our results. Complementary biomarker assessments (performed in [name] laboratory) will allow us to more comprehensively correlate biomarker changes with clinical response. The proposal also gives us the

Product: Secukinumab

Protocol Number: CAIN457AUS05T

Date: 14 July 2018

14

opportunity to validate 3 severity scales for ichthyosis, which will hugely facilitate future research and its interpretation.

1.5 Rationale for Choice of Comparator

A placebo arm is necessary to obtain reliable efficacy and safety measurements.

1.6 Risks and Benefits of Secukinumab

Previous studies using secukinumab have found the following risks associated with treatment:

- **Infections:** In clinical trials, a higher rate of infections was observed in subjects treated with secukinumab (31%) compared to placebo (18%). In trials for moderate-severe plaque psoriasis, psoriatic arthritis, and ankylosing spondylitis, higher rates of common infections such as nasopharyngitis (11.4% versus 8.6%), upper respiratory tract infection (2.5% versus 0.7%) and mucocutaneous infections with candida (1.2% versus 0.3%) were observed with secukinumab compared with placebo. Given that individuals with ichthyosis have an increased risk of staphylococcal and fungal/candidal infections of the skin, there is a possibility that there may be more skin infections (beyond the known increase in mucosal candida infections), which will require vigilance.
- **Inflammatory Bowel Disease:** Both exacerbations and new onset cases of this condition occurred in patients treated with secukinumab in trials for plaque psoriasis, psoriatic arthritis and ankylosing spondylitis
- **Hypersensitivity Reactions:** Anaphylaxis and cases of rash or urticaria occurred in secukinumab treated patients in clinical trials. The removable cap of the COSENTYX Sensoready pen and the COSENTYX prefilled syringe contains natural rubber latex which may cause an allergic reaction in latex-sensitive individuals (Novartis Full Prescribing Information 2016)
- Pharyngitis, fatigue and peripheral edema were noted more in subjects receiving 3 doses of secukinumab when compared to subjects receiving 1 or 2 doses (Papp et al 2013)
- Mild to moderate (Grade 1 or 2) neutropenia was noted in 12.1% of patients receiving regular s.c. injections of secukinumab. However, there were no AEs resulting from this neutropenia and no subjects were discontinued from treatment because of this (Rich et al 2013)
- IL-17A blockade does not appear to interfere with protective antibody levels after vaccinations such as the meningococcal vaccine or the influenza vaccine (Chioato et al 2012) when comparing antibody levels in individuals who had received secukinumab s.c. to those who did not.
- Currently, there is no evidence that secukinumab imparts an increased risk of malignancy

2. STUDY ENDPOINTS

2.1 Primary and Secondary Endpoints: Double Blind and Open-Label Phases

Primary Efficacy Endpoint: Reduction at week 16 in the Ichthyosis Area Severity Index (IASI)

Primary Safety Endpoint: Occurrence of bacterial or fungal mucocutaneous infection through week 16

Secondary Efficacy Endpoints (evaluated at weeks 8, 12, 16, 32 and 52):

Product: Secukinumab

Protocol Number: CAIN457AUS05T

Date: 14 July 2018

15

- Reduction in the IASI-E at weeks 8,12 and 16 (double blind portion)
- Reduction in IASI-S at weeks 8,12 and 16 (double blind portion)
- Reduction in CISI (Congenital Ichthyosis Severity Index) for skin redness/ erythema at weeks 8,12 and 16 (double blind portion) by subject and by physician assessors
- Reduction in CISI (Congenital Ichthyosis Severity Index) for skin hyperkeratosis/ scaling at weeks 8,12 and 16 (double blind portion) by subject and by physician assessors
- Reduction in composite and erythema scores of Yale Ichthyosis Severity Index at weeks 8,12 and 16 (double blind portion)
- Reduction in the IASI-E at weeks 32 and 52 as compared to baseline (open label portion)
- Reduction in IASI-S at weeks 32 and 52 as compared to baseline (open label portion)
- Reduction in CISI (Congenital Ichthyosis Severity Index) for skin redness/ erythema by subject and by physician assessors at weeks 32 and 52 as compared to baseline (open label portion)
- Reduction in CISI (Congenital Ichthyosis Severity Index) for skin hyperkeratosis/ scaling by subject and by physician assessors at weeks 32 and 52 as compared to baseline (open label portion)
- Reduction in composite and erythema scores of Yale Ichthyosis Severity Index at weeks 32 and 52 as compared to baseline (open label portion)
- A 2-point reduction in CISI for redness/erythema at weeks 16, 32, and 52
- A 2-point reduction in CISI for scale/hyperkeratosis at weeks 16, 32, and 52
- A 50% reduction in IASI at weeks 16, 32 and 52
- A 50% reduction in IASI-E or IASI-S at weeks 16, 32 and 52
- A 75% reduction in composite and individual IASIs at weeks 16, 32 and 52
- 50% Reduction in the Bodemer score, which heavily weighs associated morbidity (contractures, ectropion, mouth tightness, fissures) in addition to erythema, scaling and thickening (Bodemer et al. 2011) at weeks 16, 32 and 52
- A 3-point reduction in patient-reported itch and pain (each on a 10 point scale) at weeks 16, 32 and 52
- Improvement in the 5-D itch score
- Reduction in transepidermal water loss (TEWL), a functional measure of barrier, at weeks 16, 32 and 52
- Reduction in the Dermatology Life Quality Index (DLQI) at weeks 16, 32 and 52
- Reduction in the iQoL-32 index at weeks 16, 32 and 52

Reduction in the above assessments stratified by subtype, severity, and gender

These clinical indices will be assessed as per the Schedule of Assessments flowchart (Appendix 1) and require minimal input or time commitment from the study participants, but are critical to analyze trends with time.

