To compare secukinumab to placebo according to the proportion of patients who achieve IASI50/IASI75 at week 16, a Fisher's exact test for contingency tables analysis will be used. The same approach will be used for all other binary outcomes, including a 2-point reduction in CISI, 50% (or 75%) reduction in IASI-E, EASI-S, a 3-point reduction in patient-reported itch or pain (each on a 10 point scale); and a 50% reduction in TEWL.

Mechanistic Endpoints: mRNA expression values will be normalized to housekeeping gene hARP and log₂-transformed for analysis. Measurements under the limit of detections will be imputed as 20% of the minimum value observed for that gene. Similar to the IASI score, qRT-PCR expression data was modeled using a mixed effect models.

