9.4 Safety Variables

Safety will be evaluated by tabulations of adverse events and will be presented with descriptive statistics at each visit for each treatment group. The statistical evaluations will be organized by Treatment Phase (Weeks 0-16) and Crossover/Open-label phase (16-52). The number and percentage of subjects experiencing an AE/SAE will be stratified by system organ class, or a preferred term, and severity of the adverse event, and recorded and tabulated overall by each sub-strata. Each subject will be counted only once within a system organ class or a preferred term using the adverse events with the highest severity within each category. All information pertaining to adverse events noted during the study will be listed by subject, detailing verbatim given by the investigator, preferred term, system organ class, date of onset, date of resolution, severity, and relationship to treatment. A tabulation of Serious Adverse Events (SAEs), will be provided by subject within treatment groups. The proportion of subjects in each treatment group reporting adverse events that occur in ~ 5% in either treatment group will be compared using the Fisher's exact test.

The specific system organ classes and preferred terms analyzed will be those that are reported by at least five percent of the subjects in either treatment group.

9.5. Sample size Justification:

Sample size estimation for this trial is based on the comparison of the change in the composite IASI score from baseline to 16 weeks post treatment between the secukinumab and placebo arms. Data from our cohort

Product: Secukinumab

Protocol Number: CAIN457AUS05T

Date: 14 July 2018

36

of 21 adolescents and adults was used to estimate the sample size. The mean composite IASI score in this cohort was 28.9 with a standard deviation of 9.0. Assuming a correlation between the pre and post treatment IASI scores of 0.55, we estimated the standard deviation of the baseline to week 16 change at approximately 8.5. Fixing the type I error at 0.05 for a two tailed t-test, a sample size of 16 subjects per group provides 80% power to detect a treatment effect of 30% for change in the IASI composite score (40% reduction in the secukinumab vs. an 10% reduction in the placebo arm). To account for an anticipated 20% dropout rate, 20 subjects in each treatment group (total 40) will be randomized.

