Appendix 5: Bodemer Scale

Product: Secukinumab
 Protocol Number: CAIN457AUS05T
 Date: 14 July 2018

(a) BODY SURFACE AREA WITH SCALES **(b) BODY SURFACE AREA WITH ERYTHEMA**

EXTENT: A =%

EXTENT: B =%

(c) PRURITUS: (C) (Value in cm)

PRURITUS (0 – 10) 0 _____ 10
 VISUAL ANALOGUE SCALE (average for the last 3 last days and nights)

(d) SKIN PAIN: (D) (Value in cm)

SKIN PAIN (0 – 10) 0 _____ 10
 VISUAL ANALOGUE SCALE (average for the last 3 last days and nights)

(e) SEVERITY OF 10 SYMPTOMS: (E) (Cumulated severity score for 10 symptoms: total value ranging from 0 to 60)

SCORE = A/10 + B/10 + C + D + E = / 100

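### The Bodemer score has no change-in-score efficacy endpoint: its only stated efficacy endpoint is a 50% cut tested by Fisher's exact test, which would probably cost much of the power to see an effect

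*Combined protocol and SAP*

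**What the plan says.** The only efficacy endpoint that Section 2.1 states for the Bodemer score is "50% Reduction in the Bodemer score, which heavily weighs associated morbidity (contractures, ectropion, mouth tightness, fissures) in addition to erythema, scaling and thickening", at weeks 16, 32 and 52. The same list gives IASI-E, IASI-S, CISI erythema and CISI scaling both a responder cut and a reduction in score. The composite IASI has its cuts there and its change in score as the primary endpoint. Yale, TEWL, DLQI and iQoL-32 appear as reductions in score.

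Appendix 5 defines Bodemer as a sum out of 100: "SCORE = A/10 + B/10 + C + D + E = / 100". Section 6.1.9 and Appendix 1 schedule severity scoring at every visit, and Section 6.1.9 calls the Bodemer system non-validated.

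Section 9.3 assigns Fisher's exact test to IASI50 and IASI75 at week 16 and adds: "The same approach will be used for all other binary outcomes". Bodemer is not in the examples that follow but is covered by that sentence. The mixed model in Section 9.3 is written for the composite IASI and is extended by name only to the qRT-PCR expression data.

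**The concern.** A 0 to 100 score is reduced to yes or no before the arms are compared. A subject who improves by 45% then counts the same as one who does not improve. With 40 randomised subjects, Fisher's exact test on such a cut has much less power than a comparison of mean change, unless the drug effect is so large that either analysis would find it.

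The synopsis labels Bodemer the clinical burden of disease. A real fall that usually stays below 50% could therefore be reported as a non-significant responder comparison, with no planned estimate of the mean difference beside it. An analysis of mean change added after unblinding would be post hoc. The documents give no basis for choosing 50% on this scale, such as a minimal important difference.

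**Working it through.** **Inputs, all for the composite IASI (Section 9.5).** Baseline: "The mean composite IASI score in this cohort was 28.9 with a standard deviation of 9.0". The pre-to-post correlation is taken as 0.55, and the SD of change as about 8.5. Effect: "40% reduction in the secukinumab vs. an 10% reduction in the placebo arm". The design statement is "Fixing the type I error at 0.05 for a two tailed t-test, a sample size of 16 subjects per group provides 80% power", inflated to 20 per arm for 20% dropout. No corresponding Bodemer figure exists, so carrying these over is an assumption.

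**Reproducing the plan's figure.**
- SD of change = √(2 × 9.0² × (1 − 0.55)) = 8.54, stated as about 8.5.
- Difference = 0.30 × 28.9 = 8.67 points.
- Standardised difference = 8.67 / 8.5 = 1.02.
- Two-sided t-test power (noncentral t): 79.7% at 16 per arm, 88.2% at 20 per arm.
- 16 / 0.8 = 20 per arm.

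The plan's sample size reproduces. The t-test on change stands in for the mixed model below.

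**Responder power if Bodemer behaved like the composite IASI.** Power is the exact enumerated power of the two-sided 0.05 Fisher test. Φ is the standard normal distribution function.

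*Model A: cut at half the mean baseline.* SD of percent change = 8.5 / 28.9 = 29.4%.
- Secukinumab: 1 − Φ((50 − 40) / 29.4) = 36.7%.
- Placebo: 1 − Φ((50 − 10) / 29.4) = 8.7%.

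*Model B: each subject's own baseline.* Pre and post scores are bivariate normal (SD 9.0, correlation 0.55). Response means post − 0.5 × pre ≤ 0, and the SD of that quantity is 9.0 × √(1 + 0.25 − 0.55) = 7.53.
- Secukinumab: Φ(−0.10 × 28.9 / 7.53) = 35.1%.
- Placebo: Φ(−0.40 × 28.9 / 7.53) = 6.2%.

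| Model | n per arm | Fisher on 50% cut | t-test on change | Loss (points) |
|---|---|---|---|---|
| A | 16 | 33.3% | 79.7% | 46.4 |
| A | 20 | 45.8% | 88.2% | 42.4 |
| B | 16 | 38.8% | 79.7% | 41.0 |
| B | 20 | 52.7% | 88.2% | 35.5 |

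**Other assumed effects, Model A, SD held at 29.4%, 20 per arm.**

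| Mean reduction | Fisher | t-test | Loss (points) |
|---|---|---|---|
| 20% vs 10% | 4% | 18% | 14 |
| 25% vs 10% | 9% | 35% | 26 |
| 30% vs 10% | 17% | 55% | 38 |
| 40% vs 10% | 46% | 88% | 42 |
| 50% vs 10% | 79% | 99% | 20 |
| 60% vs 10% | 96% | 100% | 4 |

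**Other assumed SDs of percent change, 40% vs 10%.** For SDs from 20% to 40% the loss is 34 to 53 points at 16 per arm and about 34 to 42 points at 20 per arm. At an SD of 50% and 20 per arm it is 21% against 46%, a loss of 25 points.

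**The case against.** The strongest reply is that the plan makes no power claim for Bodemer. It is one of about 20 secondary endpoints in a pilot, on a scale the protocol is itself only trying out, and no primary conclusion depends on it. Change in DLQI and iQoL-32 are endpoints, so patient burden does not rest on Bodemer alone. All of that stands and limits the weight of the point.

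Four stronger readings are tempting, and the documents do not support them.

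- *A loss of 42 to 46 points follows from the plan's own assumptions.* Those assumptions concern the composite IASI, and that narrower range also needs a cut fixed at half the mean baseline. Using each subject's own baseline gives 35.5 to 41.0. A large gain is not assured in every scenario either: with the SD held constant it falls to 14 points for a small effect, where mean change is badly underpowered too, and to 4 points for a very large one.
- *Bodemer enters the trial only as a responder, and change is ruled out.* The score is also used in the reliability analysis (Sections 6.1.9 and 9.6). The synopsis has a general objective on reduction in other severity assessments and a general statement about mixed models for change over time, and Section 2.1 ends with a line on reductions by subgroup. None of these names an overall between-arm comparison of Bodemer change. The analysis is unspecified, not excluded.
- *There would be few or no responders in either arm.* The base case gives 36.7% and 8.7%, about 7 and 2 of 20.
- *The scale is mostly made of items that the drug cannot move.* Section 1.3 says: "We hypothesize that Th17 activation plays an important role in the erythema and possibly the thickening and scaling of ichthyosis". Erythema carries at most 16 of the 100 points (10 + 6), and retractions, functional impairment, eyelids and mouth carry 30 (5 × 6). But scaling and keratoderma carry 28 (10 + 3 × 6), itch and pain 20, and fissures 6, so 70 points are skin signs and symptoms.

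**Conclusion.** The point holds as a gap in the endpoint list. Bodemer has no change-in-score efficacy endpoint, and its stated efficacy comparison is a 50% cut with Fisher's exact test. The power cost is conditional, because the plan supplies no Bodemer mean, SD, correlation or effect. If the score behaved like the composite IASI in Section 9.5, the cost would be roughly 35 to 46 points at 16 to 20 per arm. Across the other effects tried at 20 per arm with the same SD, it ranges from about 4 to about 40 points. Change in score had the higher power in every case computed, under normal distributions and with a t-test standing in for the mixed model. This is a worthwhile and inexpensive improvement to a secondary endpoint. It is not a threat to the trial's primary conclusion.

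**What to change.** In Section 2.1, add change from baseline in the Bodemer score at week 16 for the double-blind phase, with change at weeks 32 and 52 reported descriptively. In Section 9.3, state that the week-16 change is analysed with the mixed model already planned for the composite IASI, reporting the mean difference between arms with its 95% CI. Keep the 50% responder proportion as a supportive summary. Make the change before unblinding.

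The cost is wording in two sections and one more run of a planned model. The score is already collected at every visit, so no subjects, visits or procedures are added. The small downside is that a mean difference on a non-validated scale is harder to interpret than a responder percentage, which is why the percentage is kept.
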